6.4. Part C (SEA-BCMA plus Dexamethasone)

6.4.1. Screening Visit (Days –28 to 1)

- Informed consent (Section 10.1)
- Study eligibility per inclusion/exclusion criteria (Section 4)
- Medical history (Section 7.1)
- Serology (hepatitis B, C); if hepatitis C serology is positive, HCV RNA test by PCR is required to confirm
- Plasmacytoma evaluation per institutional standard imaging modality in cases of suspected or known plasmacytoma (Section 7.1)

6.4.2. Baseline Visit (Days –7 to Day 1)

- Weight and height
- ECG in triplicate (Section 7.7.14)
- Physical examination (Section 7.1)
- ECOG performance status (Section 7.7.15 and Appendix D)
- Blood and urine samples for local laboratory assessment (Section 7.7.11)
 - Serum chemistry panel
 - CBC with differential
 - HbA1c
 - If HbA1c is elevated ($\geq 6.5\%$), refer subject to appropriate provider prior to or within 1 week of starting study treatment in Cycle 1 for glucose management).
 - Pregnancy test for subjects of childbearing potential
 - PT/PTT/INR
 - Urinalysis (microscopy required if urinalysis results are abnormal)
 - UPCR calculation via spot urine test
- Disease assessments by local laboratory (Section 7.2)
 - BM aspirate, including BM aspirate clot, and biopsy (to also be submitted for central assessment) (Window Day –10 to 1)

- SPEP/immunofixation
- UPEP/immunofixation (24-hour urine sample)
- SFLC
- Quantitative immunoglobulins
- Beta-2 microglobulin
- Skeletal survey (via whole body plain film radiography, or via whole body CT scan, to assess presence and size of lytic bony lesions)
- Blood sample for Modified SPEP for subjects with IgG myeloma only
- Blood samples for biomarkers assessments by central laboratory ([Appendix B](#))

6.4.3. Treatment Period

The treatment period is Day 1 to 28 of each cycle.

6.4.3.1. Day 1 (-1 day)

If Baseline visit activities occur the day prior to Cycle 1, Day 1, the following assessments do not need to be repeated at Cycle 1, Day 1:

- Physical examination
- Weight and height
- ECOG performance status
- Serum chemistry panel
- CBC with differential
- Urinalysis (microscopy required if urinalysis results are abnormal)
- UPCR calculation via spot urine test

Results from clinical laboratory assessments must be reviewed prior to study drug dosing.

Subjects must continue to meet eligibility prior to study drug administration on Cycle 1 Day 1.

At subsequent cycles, dose modifications should be made in accordance with Sections [5.2.3](#) and [5.7.1](#).

- Physical examination including weight
- Vital signs (Section [7.7.10](#)):
 - Predose
 - During the infusion:
 - 15 minutes after start of infusion
 - 30 minutes after start of infusion
 - 30 minute intervals during infusion and after any change in rate of infusion
 - After completion of study treatment administration:
 - Within 5 minutes

- 15 minutes after completion of infusion (Cycle 1 only)
- 30 minutes after completion of infusion (Cycle 1 only)
- 60 minutes after completion of infusion (Cycle 1 only)
- 90 minutes after completion of infusion (Cycle 1 only)
- 120 minutes after completion of infusion (Cycle 1 only)
- ECOG performance status
- Blood and urine samples for local laboratory assessment
 - CBC with differential
 - Serum chemistry panel
 - Urinalysis (microscopy required if urinalysis results are abnormal)
 - UPCR calculation via spot urine test
- Dexamethasone administration (1 to 3 hours prior to SEA-BCMA infusion)
- Administer premedication approximately 45 to 90 minutes prior to the infusion of SEA-BCMA (Section 5.5).
- SEA-BCMA administration (Section 5.2.2)
- Blood samples for PK/ATA/biomarkers assessments by central laboratory ([Appendix B](#))

6.4.3.2. Day 2

- Blood samples for PK/biomarkers assessments by central laboratory (Cycle 1; [Appendix B](#))

6.4.3.3. Day 4

- Blood samples for PK/biomarkers assessments by central laboratory (Cycle 1; [Appendix B](#))

6.4.3.4. Day 8 (± 1 day)

- Blood samples for local laboratory assessment
 - CBC with differential
 - Serum chemistry panel
- Blood samples for PK/biomarkers assessments by central laboratory (Cohort 1, Cycle 1 only; Cohort 2, Cycles 1 and 2 only; [Appendix B](#))
- Dexamethasone administration (1 to 3 hours prior to SEA-BCMA infusion, if applicable)

Part C Cohort 2, Cycles 1 and 2 only:

Laboratory results must be reviewed prior to study drug administration in order to determine whether to proceed with dosing or whether dose modification is required.

- Physical examination

- ECOG performance status
- Vital signs:
 - Predose
 - During the infusion:
 - 15 minutes after start of infusion
 - 30 minutes after start of infusion
 - 30 minute intervals during infusion and after any change in rate of infusion
 - After completion of study treatment administration:
 - Within 5 minutes
- Urine samples for local laboratory assessment
 - Urinalysis (microscopy required if urinalysis results are abnormal)
 - UPCR calculation via spot urine test
- Administer premedication approximately 45 to 90 minutes prior to the infusion of SEA-BCMA (Section [5.5](#)).
- SEA-BCMA administration (Section [5.2.2](#))

6.4.3.5. Day 15 (± 1 day)

- Blood samples for local laboratory assessment
 - CBC with differential
 - Serum chemistry panel
- Blood samples for PK/biomarkers assessments by central laboratory (Cycles 1, 2, and 3 only; [Appendix B](#))

Laboratory results must be reviewed prior to study drug administration in order to determine whether to proceed with dosing or whether dose modification is required.

- Physical examination including weight
- ECOG performance status
- Vital signs:
 - Predose
 - During the infusion:
 - 15 minutes after start of infusion
 - 30 minutes after start of infusion
 - 30 minute intervals during infusion and after any change in rate of infusion
 - After completion of study treatment administration:
 - Within 5 minutes

- Urine samples for local laboratory assessment
 - Urinalysis (microscopy required if urinalysis results are abnormal)
 - UPCR calculation via spot urine test
- Dexamethasone administration (1 to 3 hours prior to SEA-BCMA infusion)
- Administer premedication approximately 45 to 90 minutes prior to the infusion of SEA-BCMA (Section 5.5).
- SEA-BCMA administration (Section 5.2.2)

6.4.3.6. Day 22 (± 1 day)

- Response assessments by local laboratory (Day 22 to 28)
 - BM aspirate, including BM aspirate clot, and biopsy (to be also submitted for central assessment) (Cycle 2, Cycle 6, every 6 cycles thereafter, and at time of suspected CR)
 - SPEP/immunofixation
 - UPEP/immunofixation if screening UPEP ≥ 200 mg/24 hours or for assessment of VGPR or better
 - In cases of suspected or known plasmacytoma, plasmacytoma evaluation should be performed per institutional standard imaging modality every 4 cycles or to confirm a response of PR or better, or as clinically indicated to confirm PD.
 - SFLC
 - Quantitative immunoglobulins
- Blood samples for local laboratory assessment
 - CBC with differential
 - Serum chemistry panel
- Blood sample for Modified SPEP for subjects with IgG myeloma only
- Blood samples for PK/biomarkers assessments by central laboratory (Cycles 1, 2, 3, 6, and every 6 cycles thereafter, and at time of suspected CR; (Appendix B). When applicable, blood and BM samples must be collected on the same day.
- Dexamethasone administration (1 to 3 hours prior to SEA-BCMA infusion, if applicable)

Part C Cohort 2 Cycles 1 and 2 only:

Laboratory results must be reviewed prior to study drug administration in order to determine whether to proceed with dosing or whether dose modification is required.

- Physical examination
- ECOG performance status
- Vital signs:
 - Predose
 - During the infusion:

- 15 minutes after start of infusion
- 30 minutes after start of infusion
- 30 minute intervals during infusion and after any change in rate of infusion
- After completion of study treatment administration:
 - Within 5 minutes
- Urine samples for local laboratory assessment
 - Urinalysis (microscopy required if urinalysis results are abnormal)
 - UPCR calculation via spot urine test
- Administer premedication approximately 45 to 90 minutes prior to the infusion of SEA-BCMA (Section 5.5).
- SEA-BCMA administration (Section 5.2.2)

6.4.4. Qualitative Interview

Qualitative interview to be conducted within 1 cycle of the time of first OR (PR or better) or within 1 cycle of documentation of ongoing SD at the end of Cycle 4, whichever occurs first. See the Interview Guide for additional details. Qualitative interviews will be conducted in up to a total of 10 subjects from Part C and Part D.

6.5. Part D (SEA-BCMA plus Pomalidomide and Dexamethasone)

6.5.1. Screening Visit (Days -28 to 1)

- Informed consent (Section 10.1)
- Study eligibility per inclusion/exclusion criteria (Section 4)
- Medical history (Section 7.1)
- Serology (hepatitis B, C); if hepatitis C serology is positive, HCV RNA test by PCR is required to confirm
- Plasmacytoma evaluation per institutional standard imaging modality in cases of suspected or known plasmacytoma (Section 7.1)
- Pregnancy test for subjects of childbearing potential (10 to 14 days prior to planned Cycle 1 Day 1)

6.5.2. Baseline Visit (Days -10 to Day 1)

- Weight and height
- ECG in triplicate (Section 7.7.14)
- Physical examination (Section 7.1)
- ECOG performance status (Section 7.7.15 and Appendix D)
- Blood and urine samples for local laboratory assessment (Section 7.7.11)
 - Serum chemistry panel

- CBC with differential
- HbA1c
 - If HbA1c is elevated ($\geq 6.5\%$), refer subject to appropriate provider prior to or within 1 week of starting study treatment in Cycle 1 for glucose management)
- Pregnancy test for subjects of childbearing potential (within 24 hours prior to planned Cycle 1 Day 1)
- PT/PTT/INR
- Urinalysis (microscopy required if urinalysis results are abnormal)
- UPCR calculation via spot urine test
- Disease assessments by local laboratory (Section [7.2](#))
 - BM aspirate, including BM aspirate clot, and biopsy (to also be submitted for central assessment) (Window Day –10 to 1)
 - SPEP/immunofixation
 - UPEP/immunofixation (24-hour urine sample)
 - SFLC
 - Quantitative immunoglobulins
 - Beta-2 microglobulin
 - Skeletal survey (via whole body plain film radiography, or via whole body CT scan, to assess presence and size of lytic bony lesions)
- Blood sample for Modified SPEP for subjects with IgG myeloma only
- Blood samples for biomarkers assessments by central laboratory ([Appendix B](#))

6.5.3. Treatment Period

The treatment period is Day 1 to 28 of each cycle.

6.5.3.1. Day 1 (–1 day)

If Baseline visit activities occur the day prior to Cycle 1, Day 1, the following assessments do not need to be repeated at Cycle 1, Day 1:

- Physical examination
- Weight and height
- ECOG performance status
- Serum chemistry panel
- CBC with differential
- Urinalysis (microscopy required if urinalysis results are abnormal)
- UPCR calculation via spot urine test

Results from clinical laboratory assessments must be reviewed prior to study drug dosing. Subjects must continue to meet eligibility prior to study drug administration on Cycle 1 Day 1. At subsequent cycles, dose modifications should be made in accordance with Sections [5.2.3](#) and [5.7.1](#).

- Pregnancy test for subjects of childbearing potential
- Physical examination including weight
- Vital signs (Section [7.7.10](#)):
 - Predose
 - During the infusion:
 - 15 minutes after start of infusion
 - 30 minutes after start of infusion
 - 30 minute intervals during infusion and after any change in rate of infusion
 - After completion of study treatment administration:
 - Within 5 minutes
 - 15 minutes after completion of infusion (Cycle 1 only)
 - 30 minutes after completion of infusion (Cycle 1 only)
 - 60 minutes after completion of infusion (Cycle 1 only)
 - 90 minutes after completion of infusion (Cycle 1 only)
 - 120 minutes after completion of infusion (Cycle 1 only)
- ECOG performance status
- Blood and urine samples for local laboratory assessment
 - CBC with differential
 - Serum chemistry panel
 - Urinalysis (microscopy required if urinalysis results are abnormal)
 - UPCR calculation via spot urine test
- Dexamethasone administration (1 to 3 hours prior to SEA-BCMA infusion)
- Pomalidomide administration (1 to 3 hours prior to SEA-BCMA infusion on Cycle 1 Day 1), and then daily self-administration thereafter on Days 2 to 21
- Administer premedication approximately 45 to 90 minutes prior to the infusion of SEA-BCMA (Section [5.5](#))
- SEA-BCMA administration (Section [5.2.2](#))
- Blood samples for PK/ATA/biomarkers assessments by central laboratory ([Appendix B](#))

6.5.3.2. Day 2

- Blood samples for PK/biomarkers assessments by central laboratory (Cycle 1; [Appendix B](#))

6.5.3.3. Day 4

- Blood samples for PK/biomarkers assessments by central laboratory (Cycle 1; [Appendix B](#))

6.5.3.4. Day 8 (± 1 day)

- Blood samples for local laboratory assessment
 - CBC with differential
 - Serum chemistry panel
- Blood samples for PK/biomarkers assessments by central laboratory (Cycle 1; [Appendix B](#))
- Dexamethasone administration (1 to 3 hours prior to SEA-BCMA administration)

6.5.3.5. Day 15 (± 1 day)

- Blood samples for local laboratory assessment
 - CBC with differential
 - Serum chemistry panel
- Blood samples for PK/biomarkers assessments by central laboratory (Cycles 1, 2, and 3 only; [Appendix B](#))

Laboratory results must be reviewed prior to study drug administration in order to determine whether to proceed with dosing or whether dose modification is required.

- Pregnancy test for subjects of childbearing potential
- Physical examination including weight
- ECOG performance status
- Vital signs:
 - Predose
 - During the infusion:
 - 15 minutes after start of infusion
 - 30 minutes after start of infusion
 - 30 minute intervals during infusion and after any change in rate of infusion
 - After completion of study treatment administration:
 - Within 5 minutes
- Urine samples for local laboratory assessment

- Urinalysis (microscopy required if urinalysis results are abnormal)
- UPCR calculation via spot urine test
- Dexamethasone administration (1 to 3 hours prior to SEA-BCMA infusion)
- Administer premedication approximately 45 to 90 minutes prior to the infusion of SEA-BCMA (Section 5.5).
- SEA-BCMA administration (Section 5.2.2)

6.5.3.6. Day 22 (± 1 day)

- Response assessments by local laboratory (Day 22 to 28)
 - BM aspirate, including BM aspirate clot, and biopsy (to be also submitted for central assessment) (Cycle 2, Cycle 6, every 6 cycles thereafter, and at time of suspected CR)
 - SPEP/immunofixation
 - UPEP/immunofixation if screening UPEP ≥ 200 mg/24 hours or for assessment of VGPR or better
 - In cases of suspected or known plasmacytoma, plasmacytoma evaluation should be performed per institutional standard imaging modality every 4 cycles or to confirm a response of PR or better, or as clinically indicated to confirm PD.
 - SFLC
 - Quantitative immunoglobulins
- Blood samples for local laboratory assessment
 - CBC with differential
 - Serum chemistry panel
- Blood sample for Modified SPEP for subjects with IgG myeloma only
- Blood samples for PK/biomarkers assessments by central laboratory (Cycles 1, 2, 3, 6, and every 6 cycles thereafter, and at time of suspected CR; Appendix B). When applicable, blood and BM samples must be collected on the same day.
- Dexamethasone administration (1 to 3 hours prior to SEA-BCMA administration)

6.5.4. Qualitative Interview

Qualitative interview to be conducted within 1 cycle of the time of first OR (PR or better). See the Interview Guide for additional details. Qualitative interviews will be conducted in up to a total of 10 subjects from Part C and Part D.

6.6. Complete Response Assessment

- BM aspirate (and BM biopsy, if available) in subjects with a negative blood and urine M-protein (to be submitted for central assessment of markers of drug activity and resistance to SEA-BCMA)
- Blood samples for biomarkers assessments by central laboratory (Appendix B)

- 24-hour urine sample for UPEP/immunofixation
- Plasmacytoma evaluation, per institutional standard imaging modality, for subjects with plasmacytomas at baseline

6.7. Evaluation of Infusion/Hypersensitivity Reactions (Part A only)

Subjects in Part A experiencing a \geq Grade 3 infusion reaction or delayed hypersensitivity reaction must have an IHR visit and an IHR Follow-up visit.

6.8. Infusion/Hypersensitivity Reaction Visit (Part A only)

For subjects in Part A, if the IHR occurs on the day of infusion, perform the IHR visit that day. If a delayed hypersensitivity reaction occurs, the IHR visit should be performed as soon as possible, preferably within 24 hours, but not more than 72 hours after occurrence.

The following assessments will be performed:

- Physical exam
- Vital signs
- Blood and urine samples by local laboratory
 - CBC with differential
 - Serum chemistry panel
 - Urinalysis (microscopy required if urinalysis results are abnormal)
- Blood sample collection for PK/biomarkers assessments by central laboratory ([Appendix B](#))

Timing of the IHR visit blood draw may overlap with another protocol-defined blood draw (ie, 2 or 6 hours postdose, or other PK/biomarkers sampling time points). If this occurs, collect blood samples for the IHR visit; lab tests for the protocol-defined blood draw do not need to be duplicated if they are collected as part of the IHR visit. For example, if the IHR visit takes place 2 hours postdose, a separate blood draw for the protocol-defined 2-hour postdose PK/biomarkers blood draw is not required, because samples for Biomarker analyses will be collected as part of the IHR visit.

Similarly, a subject may experience a delayed hypersensitivity reaction so that the IHR visit takes place on Day 8. If this occurs, collect blood samples for the IHR visit. The protocol-defined Day 8 local labs (CBC and chemistry panel) do not need to be duplicated because they are collected as part of the IHR visit. The central lab Biomarkers blood tests (PK, immunophenotyping, cytokine, soluble target and ligands, PBMCs) do not need to be duplicated provided they are collected within the protocol-defined PK/biomarkers blood draw window.

6.9. Infusion/Hypersensitivity Reaction Follow-up Visit (24 to 72 hours; Part A only)

For subjects in Part A, the IHR Follow-up visit is scheduled 24-72 hours after the initial IHR visit, and the following assessments are performed:

- Physical exam

- Vital signs
- Blood and urine samples by local laboratory
 - CBC with differential
 - Serum chemistry panel
 - Urinalysis (microscopy required if urinalysis results are abnormal)
- Blood sample collection for PK/biomarkers assessment by central laboratory ([Appendix B](#))

Timing of the IHR Follow-up visit blood draw may overlap with another protocol-defined blood draw. If this occurs, collect blood samples for the IHR Follow-up visit local and central labs as required; lab tests for the protocol-defined blood draw do not need to be duplicated if they are collected as part of the IHR Follow-up visit.

6.10. End of Treatment Visit (30 to 37 days after last dose of study drug)

EOT visits should occur 30 to 37 days after the last dose of study drug unless delayed due to an AE. Note: EOT evaluations must be performed before initiation of a new therapy. If EOT evaluations are completed before 30 days after the last study treatment, the subject will be contacted 30 to 37 days following the last treatment to assess for AEs.

- ECG in triplicate
- Physical examination
- ECOG performance status
- Vital signs
- Weight
- Pregnancy test for subjects of childbearing potential
- Blood and urine samples for local laboratory assessment
 - CBC with differential
 - Serum chemistry panel
 - Urinalysis (microscopy required if urinalysis results are abnormal)
 - UPCR calculation via spot urine test (only required if not conducted within 4 weeks prior to EOT)
- Response assessments by local laboratory
 - SFLC
 - BM aspirate and biopsy, if collected per SOC, or to confirm CR, to be submitted for central assessment of markers of drug activity and resistance to SEA-BCMA
 - SPEP/immunofixation
 - UPEP/immunofixation

- In cases of suspected or known plasmacytoma, plasmacytoma evaluation, per institutional standard imaging modality, should be performed every 4 cycles or to confirm a response of PR or better, or as clinically indicated to confirm PD.
- Quantitative immunoglobulins
- Blood sample for Modified SPEP for subjects with IgG myeloma only
- Blood samples for PK/ATA/biomarkers assessments by central laboratory ([Appendix B](#))

6.11. Follow-up (every 12 weeks ±2 weeks)

Subjects who discontinue from treatment with SEA-BCMA will remain on the study for follow-up until withdrawal of consent, death, or study closure, whichever occurs first.

The first follow-up visit will occur 12 weeks (±2 weeks) from the most recent prior response evaluation. Subsequent follow-up visits will be scheduled for 12 weeks (±2 weeks) from the previous follow-up visit.

Subjects who discontinue treatment due to PD or who have initiated subsequent therapy will not be assessed for response but will be followed for survival. Subjects who discontinue treatment will continue to be assessed for response after EOT until PD or initiation of a new therapy. These subjects will be followed at this schedule until withdrawal of consent, death, or study closure, whichever occurs first.

The following assessments will be performed until disease progression or initiation of subsequent therapy; subjects will be followed for survival thereafter.

- Blood samples for local laboratory assessment (obtain until disease progression or until initiation of subsequent anticancer therapy)
 - CBC with differential
 - Serum chemistry panel
- Response assessments by local laboratory
 - SFLC
 - SPEP/immunofixation
 - UPEP/immunofixation if measurable disease in urine
 - BM aspirate and biopsy (for confirmation of CR) (to be submitted for central assessment of markers of response)
 - In cases of suspected or known plasmacytoma, plasmacytoma evaluation, per institutional standard imaging modality, should be performed every 4 cycles or to confirm a response of PR or better, or as clinically indicated to confirm PD.
- Blood sample for Modified SPEP for subjects with IgG myeloma only (to be collected only until subsequent therapy is initiated)
- Survival status and collection of first subsequent anticancer treatment information until death or study closure

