4.1. Inclusion Criteria

1. Diagnosis of MM requiring systemic therapy as defined by IMWG 2014 criteria ([Kumar 2016](#)).
2. Subjects must have MM that is relapsed or refractory and must be a candidate for SEA-BCMA treatment in the opinion of the treating physician.
 - a. Part A: Subjects must not have other therapeutic options known to provide clinical benefit in MM available. Subjects' prior lines of therapy must include at least a PI, an IMiD, and an anti-CD38 antibody in any order during the course of treatment. Subjects who could not tolerate a PI, IMiD, or anti-CD38 antibody are allowed.
 - b. Parts B and C: Subjects must not have other therapeutic options known to provide clinical benefit in MM available. Subjects must have received at least 3 prior lines of antimyeloma therapy and must be refractory to at least 1 agent in each of the following classes: PI, IMiD, and an anti-CD38 antibody. Prior BCMA-directed myeloma therapy, excluding prior treatment with SEA-BCMA, is permitted (eg, ADC, CAR-T cell therapy, or bispecific antibody targeting BCMA) provided that at least 3 months will have elapsed from the last dose of prior BCMA targeting therapy and Cycle 1 Day 1 of this study, and that the subject has recovered from any clinically significant toxicity of the prior BCMA-targeting therapy.
 - c. Part D: Subjects must have received at least 3 prior lines of antimyeloma therapy, including a PI, IMiD, and an anti-CD38 antibody, and must have documented IMWG disease progression on or within 60 days of completion of their last treatment. Subjects with a history of ASCT are eligible if the date of transplant was at least 12 weeks prior to initiation of SEA-BCMA treatment. Part D will be conducted in the US only.
3. Measurable disease, as defined by one or more of the following:
 - a. Serum monoclonal paraprotein (M-protein) level ≥ 0.5 g/dL; for IgA or IgD myeloma subjects, serum IgA or serum IgD ≥ 0.5 g/dL is acceptable
 - b. Urine M-protein level ≥ 200 mg/24 hr
 - c. Serum immunoglobulin FLC ≥ 10 mg/dL and abnormal serum immunoglobulin kappa lambda FLC ratio
4. Age 18 years or older.
5. An Eastern Cooperative Oncology Group (ECOG) Performance Status score of 0 or 1 (see [Appendix D](#) for conversion of performance status using Karnofsky and Lansky scales, if applicable)

6. Life-expectancy of >3 months in the opinion of the investigator

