7.2. Response/Efficacy Assessments

Response assessment includes SPEP/immunofixation, UPEP/immunofixation (in subjects with a baseline urine M-protein ≥ 200 mg/24 hour or for assessment of VGPR or better), SFLC, quantitative immunoglobulins, and plasmacytoma evaluation, per institutional standard imaging

modality (at baseline, every 4 cycles, and at additional timepoints if clinically indicated). These samples will be collected for local assessment at the times provided in [Appendix A](#). In addition, blood will be analyzed in the central laboratory using a modified SPEP for subjects with IgG myeloma.

BM aspirate, including a BM aspirate clot, and biopsy are required as part of the baseline visit, Day 22 to 28 of Cycle 2, and to confirm CR in subjects negative for blood and urine M-protein. In Part B, Part C, and Part D, BM aspirate and biopsy are also required in Cycle 6 and every 6 cycles thereafter. Both BM aspirate and biopsy samples will be assessed locally at the site for clinical evaluation. In addition, biomarker analyses will be performed centrally on these samples (see Section [7.5](#)). Any additional BM aspirates and biopsies collected at any other time while on the trial may also be submitted for central assessment.

The BM specimens will be tested centrally for assessment of response/resistance to SEA-BCMA and may include but are not limited to: evaluation of BCMA expression, immune activation, disease risk profiling, gene expression profiling, and MRD assessment.

The determination of antitumor activity will be based on response assessments made according to the 2016 IMWG Criteria ([Kumar 2016](#)) (see [Appendix J](#)). Treatment decisions by the investigator will be based on these assessments. Clinical response of stringent complete response (sCR), CR, VGPR, PR, SD, and PD will be determined at each assessment based on local laboratory (and the modified SPEP run by the central laboratory for subjects with IgG MM), radiological, and clinical evaluations. PD is based on IMWG 2016 criteria and/or clinical disease progression per investigator. All IMWG responses must be confirmed responses. When applicable, determination of immunophenotypic CR, MRD status, and minimal response will be made per the IMWG 2016 criteria.

Subjects' clinical data must be available for CRF source verification. Copies of tumor images must be made available for review by the sponsor (or its designee), upon request.

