a All response categories require 2 consecutive assessments made at any time before the institution of any new therapy; all categories also require no known evidence of progressive or new bone lesions if radiographic studies were performed. Radiographic studies are not required to satisfy these response requirements. Bone marrow assessments need not be confirmed.

b Note clarification to IMWG criteria for coding CR and VGPR in subjects in whom the only measurable disease is by serum FLC levels: CR in such subjects is defined as a normal FLC ratio of 0.26 to 1.65 in addition to CR criteria listed above. VGPR in such subjects is defined as a >90% decrease in the difference between involved and uninvolved FLC levels.

c Presence or absence of clonal cells is based upon the κ/λ ratio. An abnormal κ/λ ratio by immunohistochemistry and/or immunofluorescence requires a minimum of 100 plasma cells for analysis. An abnormal ratio reflecting presence of an abnormal clone is κ/λ of >4:1 or <1:2.

d For progressive disease, serum M-component increase of ≥ 1 g/dL is sufficient to define progression if starting M-component is ≥5 g/dL

Note: for IgA and IgD myelomas, quantitative immunoglobulin measurements are preferred for disease assessments; the same percentage change applies as for serum M-spike

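### Off-treatment follow-up omits quantitative immunoglobulins, the marker Appendix J prefers for IgA and IgD myeloma, so biochemical progression in some of these subjects may be detected late or censored

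*Protocol*

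**What the plan says.** Subjects who leave treatment without progression stay under response assessment. Protocol Section 6.11 says "Subjects who discontinue treatment will continue to be assessed for response after EOT until PD or initiation of a new therapy", and sets the interval: "Subsequent follow-up visits will be scheduled for 12 weeks (±2 weeks) from the previous follow-up visit". The response tests it lists are serum free light chains, serum electrophoresis with immunofixation, urine electrophoresis ("UPEP/immunofixation if measurable disease in urine"), bone marrow to confirm CR, and plasmacytoma evaluation where a plasmacytoma is known or suspected. Modified SPEP is also kept for IgG myeloma. Quantitative immunoglobulins are not listed.

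Three other places give that test a role in measuring disease:

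- Section 7.2 includes it in the definition of response assessment: "SFLC, quantitative immunoglobulins, and plasmacytoma evaluation".
- Inclusion criterion 3a (Section 4.1), on measurable disease, says that "for IgA or IgD myeloma subjects, serum IgA or serum IgD ≥ 0.5 g/dL is acceptable".
- The closing note of Appendix J says that "for IgA and IgD myelomas, quantitative immunoglobulin measurements are preferred for disease assessments", and applies the same percentage changes as for the M-spike.

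Appendix J defines biochemical progression as a 25% increase from the lowest value, with a minimum absolute increase. PFS and duration of response are secondary endpoints (Table 1). Protocol Sections 9.2.3 and 9.2.5 and SAP Sections 6.5.1.3 and 6.5.1.4 censor subjects without progression at the last disease assessment that documents its absence.

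**The concern.** For an IgA or IgD subject followed on the immunoglobulin level, the baseline and nadir are set on one marker, and that marker is then no longer collected once treatment stops. The subject may have stopped for toxicity or by choice and still be at risk of the PFS or duration-of-response event. If nothing else in the follow-up panel can show a 25% rise, biochemical progression is recorded only when it appears by another route, or the subject is carried forward as progression-free and censored. Ascertainment would then depend on isotype, because Section 6.11 keeps a dedicated assay for IgG subjects but drops the preferred one for IgA and IgD. Progression after stopping treatment also bears on retreatment under Section 3.1.7, so its detection matters beyond the Kaplan-Meier summaries.

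**Working it through.** The plan states no figure to reproduce here. The check sets the schedule against the progression criteria.

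**1. Where each marker is collected** (Sections 6.2 to 6.5, 6.10 and 6.11, and the four Appendix A schedules)

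| Test | Baseline | Days 22 to 28 of each cycle | EOT | Long-term follow-up |
|---|---|---|---|---|
| Serum electrophoresis/immunofixation | yes | yes | yes | yes |
| Urine electrophoresis/immunofixation | yes | conditional | yes | if measurable in urine |
| Serum free light chains | yes | yes | yes | yes |
| Modified SPEP, IgG only (Section 6) | yes | yes | yes | yes |
| Quantitative immunoglobulins | yes | yes | yes | **no** |

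In all four Appendix A schedules the follow-up cell for quantitative immunoglobulins is empty, while electrophoresis (serum and urine) and free light chains carry an X with footnote F (until progression or subsequent therapy). The Section 6.11 text and the four tables agree, so this is not one broken table cell. No other section restores the test.

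**2. What can still show progression off treatment** (Appendix J, Sections 6.11, 7.2 and 7.7.11)

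- Serum M-component: usable if the subject has a quantifiable spike, since electrophoresis is done throughout and supplies its own nadir.
- Urine M-component: only if urine disease is measurable.
- Free light chains: these count only when neither serum nor urine M-protein is measurable. The protocol does not say whether entry on serum IgA or IgD counts as measurable serum M-protein.
- Marrow plasma cells: follow-up marrow is taken to confirm CR, not to look for progression.
- Calcium: in the chemistry panel, drawn at follow-up.
- Bone lesions and plasmacytomas: skeletal survey if clinically indicated; plasmacytoma imaging if known or suspected.
- Clinical progression declared by the investigator: accepted by Section 7.2 and SAP Section 5.5.

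**3. Who is exposed.** A subject must have IgA or IgD myeloma, stop treatment without progression, and not yet have started new therapy. Exposure is greatest where there is no quantifiable spike, and greater still if free light chains are uninformative or not admissible.

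**4. Size of a delay.** Using the SAP conversion of 30.4375 days per month:

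- 12 weeks: 84 / 30.4375 = 2.8 months
- 10 weeks: 70 / 30.4375 = 2.3 months
- 14 weeks: 98 / 30.4375 = 3.2 months

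Each visit at which progression is present but not seen therefore postpones its recording by about 2.8 months (2.3 to 3.2).

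**5. How many.** The documents give no isotype split. If 10% to 25% of subjects had IgA or IgD disease (an assumption), a 20-subject cohort would hold 0.10 × 20 = 2 to 0.25 × 20 = 5 of them. That is the pool before the conditions in step 3, none of which can be quantified from the documents. The number exposed in a cohort could be none or one.

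**6. Direction.** If a visit without the marker is accepted as documenting no progression, the event or the censoring date moves later and the time is lengthened. If the visit is judged not to document absence of progression, censoring could fall back to EOT, when immunoglobulins were last drawn. That is early and possibly informative censoring. The first is the likelier handling, because Section 6.11 presents these visits as response assessments.

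**The case against.** The strongest reply is that the plan still follows these subjects with several tools. Electrophoresis is done at every assessment for every isotype. Appendix J writes progression in terms of serum M-component and calls immunoglobulins preferred, not mandatory. Criterion 3a makes serum IgA or IgD an acceptable alternative and does not imply that the subject lacks a spike. The free light chain rule is written for subjects without measurable M-protein, which may largely be the group at issue. Nothing forbids an unscheduled IgA test. The analyses are descriptive with no formal hypothesis, and dose decisions rest mainly on DLTs and safety.

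Much of this stands, and it limits the point. A reader might infer that the 25% rise cannot be computed for any IgA or IgD subject off treatment; the documents do not support that, because a subject with a quantifiable spike keeps a valid electrophoresis series. A reader might also infer a delay of at least 12 weeks; the window makes it 10 to 14. Nor is a longer PFS certain, given the two censoring readings above.

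What does not stand is that the gap is harmless. The free light chain route has an unresolved eligibility condition, marrow and skeletal survey are not routine in follow-up, and clinical progression tends to come later than biochemical progression. An optional unscheduled test does not replace a scheduled one.

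**Conclusion.** The omission is established: the protocol requires response assessment until progression or new therapy, and for IgA/IgD subjects drops the marker it prefers for that purpose. The consequence is confined to those who stop treatment without progression, chiefly those without a quantifiable serum spike. For them, biochemical progression may be recorded late, by about one visit interval per missed visit, or be censored. PFS and duration of response can be distorted, most likely upward.

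The size across a cohort cannot be calculated from the documents. It is tempting to read the 2 to 5 subjects in 20 as the number affected, but that figure rests on an assumed isotype share and precedes every other condition; the true number is probably small. It is also tempting to set one visit interval against the 3.7-month median PFS that Section 1.1 cites from the selinexor-dexamethasone trial. That shows a delay would matter for an individual, but it is not an estimate of bias in a cohort median. The primary safety objectives are not affected. This is an inexpensive improvement to two secondary endpoints.

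**What to change.** Add quantitative immunoglobulins, at least for IgA and IgD subjects, to the response assessments in Section 6.11. Enter X with footnote F in the long-term follow-up cell of that row in Appendix A, Parts A to D. State in Section 7.2 or Appendix J that the marker used for baseline and nadir is also used to judge progression in follow-up. Align SAP Section 6.5, whose list of response data to be listed also omits the test.

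The cost is one added local assay on blood already drawn at the 12-weekly visit, and a few lines of text. No visit or procedure is added.

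The SAP is dated August 2023 and already describes choices made for the final study report, so follow-up may have closed. In that case, identify the IgA/IgD subjects who left treatment without progression and were followed without the test. Report their number, and repeat the PFS and duration-of-response analyses with those subjects censored at their last quantitative immunoglobulin assessment. This cannot recover missed events, and the censoring may itself be informative, but it shows how far the estimates depend on visits that lacked the preferred marker.
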